**Check All That Apply**

 Informed Consent Form (and/or Parental Permission Form and/or translated short form)
 Assent Form
 Cover Letter (for survey/questionnaire research)
 Phone Script
 Informed Consent/HIPAA Combined Form
 Debriefing and/or Permission to Use Data Form
 Reliance Consent Form
 Sponsor's sample consent form for Dept. of Health and Human Services (DHHS)-approved protocol
 Stamped Consent Doc(s) Not Needed

Attachments

Attach Type	File Name
Informed Consent/HIPAA Combined Form	Informed ConsentHIPAA Combined Form_08.11.2022.pdf

Informed Consent Process:

Using active voice, describe how investigators will obtain consent/assent. Include:

- the circumstances under which consent will be sought and obtained
- the timing of the consent process (including any waiting period between providing information and obtaining consent)
- who will seek consent
- how you will minimize the possibility of coercion or undue influence
- the method used for documenting consent
- if applicable, who is authorized to provide permission or consent on behalf of the subject
- if applicable, specific instruments or techniques to assess and confirm potential subjects' understanding of the information

Note: all individuals authorized to obtain informed consent should be designated as such in the E-IRB "Study Personnel" section of this application.

Special considerations may include:

- Obtaining consent/assent for special populations such as children, prisoners, or people with impaired decisional capacity
- *Research Involving Emancipated Individuals*
If you plan to enroll some or all prospective subjects as emancipated, consult with UK legal counsel **prior to submitting this application to the IRB**. Include research legal counsel's recommendations in the "Additional Information" section as a separate document.
- *Research Involving Non-English Speaking Subjects*
For information on inclusion of non-English speaking subjects, or subjects from a foreign culture, see IRB Application Instructions for Recruiting Non-English Speaking Participants or Participants from a Foreign Culture.
- *Research Repositories*
If the purpose of this submission is to establish a research repository describe the informed consent process. For guidance regarding consent issues, process approaches, and sample language see the [Sample Repository/Registry/Bank Consent Template](#).

PROSPECTIVE SECTION:

We will recruit participants from the consecutive patients referred to the Orofacial Pain Clinic (OFCP) for the management of obstructive sleep apnea (OSA) with a mandibular advancement device (MAD). As part of the standard clinical protocols, these patients are initially evaluated for eligibility to start OSA therapy with a mandibular advancement device by the residents under supervision of an attending provider of the Orofacial Pain Division (College of Dentistry – University of Kentucky) at the OFPC. After the evaluation, if the patient is eligible to start MAD therapy, the study will be offered as an option for their treatment or they can continue with the standard of care provided at the clinic. If the patient expresses interest in participating in the study, they will be evaluated for eligibility by having an initial assessment done by [name] [name], [name] [name] or by [name] [name]. If the patient is eligible and agrees verbally to participate, they will be given the consent form to read.

The consent form will be offered electronically (in-person) using an iPad associated to EPIC (UK Healthcare). The patient will be allowed to take as much time as needed to read the information and a printed copy will be provided (contact information included in the copy). The patient will sign the electronic form using a digital signature on the iPad (in-person), or in paper format if any technical difficulty occurs. The hand-signed consent forms will be stored at the OFP clinic along with the rest of the paper data collection forms (locker Kentucky Clinic room E214). Only English speaking subjects will be considered as potential participants. Consequently, the consent form will be available in an English version only. If English is a second-language for the prospective subject, only those who routinely read and sign UK Healthcare documents in English will be considered eligible. During the recruitment process, the subject will be evaluated by the investigator(s) present for comprehension and will be asked to paraphrase their understanding of different aspects of the study (i.e. objectives of the study, potential risks, procedures, etc.). If patient demonstrates inadequate comprehension, they will not be considered eligible to participate in the study.

RETROSPECTIVE SECTION:

Archival data will be extracted from the records of patients that started MAD therapy for OSA at the Orofacial Pain Clinic (University of Kentucky) between 01/01/2010 and 08/17/2021. An active study involving MAD therapy outcomes (protocol #46643; same PI, [name] [name]) includes a consent form for the retrospective participants to collect retrospective data that allows to use the obtained data in future research projects.

For the prospective section, the copy of the consent form that will be provided to the participants will include the the following information:

- PI: [name] [name]: [name]; UK Kentucky Clinic, [name].
- ORI/IRB between business hours of 8 am and 5 pm EST, Monday- Friday at [name] or toll free at [name].

For the retrospective section, since this is a retrospective chart review, we do not anticipate having to address participant complaints.

Request for Waiver of Informed Consent Process

If you are requesting IRB approval to waive the requirement for the informed consent process, or to alter some or all of the elements of informed consent, complete, Section 1 and Section 2 below.

Note: The IRB does not approve waiver or alteration of the consent process for greater than minimal risk research, except

for planned emergency/acute care research as provided under FDA regulations. Contact ORI for regulations that apply to single emergency use waiver or acute care research waiver [contact]).

SECTION 1.

Check the appropriate item:

I am requesting a waiver of the requirement for the informed consent process.

I am requesting an alteration of the informed consent process.

If you checked the box for this item, describe which elements of consent will be altered and/or omitted, and justify the alteration.

SECTION 2.

Explain how each condition applies to your research.

a) The research involves no more than minimal risk to the subject.

b) The rights and welfare of subjects will not be adversely affected.

c) The research could not practicably be carried out without the requested waiver or alteration.

d) Whenever possible, the subjects or legally authorized representatives will be provided with additional pertinent information after they have participated in the study.

e) If the research involves using or accessing identifiable private information or identifiable biospecimens, the research could not practicably be carried out without using such information or biospecimens in an identifiable format.

- Private information/specimens are “identifiable” if the investigator may ascertain the identity of the subject or if identifiers are associated with the information (e.g., medical records). This could be any of the [18 HIPAA identifiers](#) including [dates of service](#).

- If not using identifiable private information or identifiable biospecimens, insert N/A below.

Request for Waiver of Signatures

If you are requesting IRB approval to waive the requirement for signatures on informed consent forms, **your research activities must fit into one of three regulatory options:**

1. The only record linking the participant and the research would be the consent document, and the principal risk would be potential harm resulting from a breach of confidentiality (e.g., a study that involves participants who use illegal drugs).
2. The research presents no more than minimal risk to the participant and involves no procedures for which written consent is normally required outside of the research context (e.g., a cover letter on a survey, or a phone script).
3. The participant (or legally authorized representative) is a member of a distinct cultural group or community in which signing forms is not the norm, the research presents no more than minimal risk to the subject, and there is an appropriate alternative mechanism for documenting that informed consent was obtained.

Select the option below that best fits your study.

*If the IRB approves a waiver of signatures, participants must still be provided oral or written information about the study. To ensure you include required elements in your consent document, use the **Cover Letter Template** as a guide. There is an [English](#) and a [Spanish](#) version.*

Option 1

Describe how your study meets these criteria:

- a) The only record linking the participant and the research would be the consent document:
- b) The principal risk would be potential harm resulting from a breach of confidentiality (i.e., a study that involves subjects who use illegal drugs).

Under this option, each participant (or legally authorized representative) must be asked whether (s)he wants to sign a consent document; if the participant agrees to sign a consent document, only an IRB approved version should be used.

Option 2

Describe how your study meets these criteria:

- a) The research presents no more than minimal risk to the participant:
- b) Involves no procedures for which written consent is normally required outside of the research context (i.e. a cover letter on a survey, or a phone script):

Option 3

Describe how your study meets these criteria:

- a) The subject (or legally authorized representative) is a member of a distinct cultural group or community in which signing forms is not the norm.
- b) The research presents no more than minimal risk to the subject.
- c) There is an appropriate alternative mechanism for documenting that informed consent was obtained.

STUDY PERSONNEL

0 unresolved comment(s)

Do you have study personnel who will be assisting with the research?

After selecting 'Yes' or 'No' you must click the 'Save Study Personnel Information' button.  Yes No

Manage Study Personnel

Identify other study personnel assisting in research project:

- The individual listed as PI in the 'PI Contact Information' section should NOT be added to this section.

- Use one of the attachment buttons in this section or under the Additional Information section to include supplemental information with your application. During the document upload process, you will be able to provide a brief description of the attachment.

Background

Include a brief review of existing literature in the area of your research. You should identify gaps in knowledge that should be addressed and explain how your research will address those gaps or contribute to existing knowledge in this area. For interventional research, search PubMed and ClinicalTrials.gov for duplicative ongoing and completed trials with same condition and intervention(s).

Multiple mandibular advancement devices (MAD) are available on the market and have been used for the management of obstructive sleep apnea (OSA). They are specifically used to prevent upper airway collapse by protruding the mandible forward, thus altering the jaw and tongue position. The models vary regarding the titrability and the level of customization [1]. Titratable devices are thought to increase treatment success by allowing gradual adaptation to optimal protrusion [2] [3]. The effective degree of mandibular protrusion used in published studies has been highly variable, ranging from 50% to 80% of maximal protrusion [1] [4] [5] [6]. In mild to moderate cases of OSA, no differences were found between 50% and 75% of protrusion [5], whereas in severe cases of OSA, 75% of protrusion demonstrated to be more efficacious than 50% [6].

Oral appliance therapy has been associated with various short and long-term side effects. In relation to the short-term adverse effects: hyper-salivation [7], dry mouth [7], dental pain [7], gingival irritation [7], and temporomandibular disorders [7] [8] has been reported at an incidence rate ranging between 6% to 86%. The long-term side effects include: temporomandibular disorders [7] [8], occlusal changes (ie: a reduction in overjet [9] [10], overbite [9] [10], and development of posterior open bite [8] [10] among others) and range between 0% and 75% of patients [7] [9] [10]. In a recent meta-analysis, the odds of experiencing a side effect leading to discontinuation of therapy with an oral appliances was 6.65:1 (95% CI) [1]. In previous studies, it has been demonstrated that an increase in side effects could be expected at larger advancement levels [11] [12], especially with more than 50% of mandibular protrusion [11]. Therefore, having a MAD design that requires less degree of mandibular advancement to reach an adequate management of OSA represents a great benefit for the patients, and can lead to better compliance.

In the case of the Orthoapnea NOA® device, the customization level is reached with a personalized approach based on clinical pictures, digital dental scans, and radiographic studies. Therefore, this allows a design that guides the mouth opening with a forward mandibular motion. The main target is to move the jaw forward progressively, so that the more the mouth is opened, the more forward the mandible can be positioned. Therefore, the Orthoapnea NOA® device is thought to require a less degree of advancement to be effective in the management of OSA than other designs. Consequently, comparing this particular characteristic of the Orthoapnea NOA® with the other available device design is hypothesized to be correlated with a lower incidence of side effects and better patient compliance.

FDA approved use: "NOA SLEEP APNEA AND SNORING DEVICE is a mandibular advance device (MAD) indicated for obstructive sleep apnea (OSA) and to alleviate or reduce snoring in adults." (FDA K202651 ; https://www.accessdata.fda.gov/cdrh_docs/pdf20/K202651.pdf). See attachments.

REFERENCES:

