Describe the characteristics of the subject population, including age range, gender, ethnic background and health status. Identify the criteria for inclusion and exclusion.

Provide the following information:

- A description of the subject selection criteria and rationale for selection in terms of the scientific objectives and proposed study design;
- A compelling rationale for proposed exclusion of any sex/gender or racial/ethnic group;
- Justification for the inclusion of vulnerable groups such as children, prisoners, adults with impaired consent capacity, or others who may be vulnerable to coercion or undue influence.

Please consider these resources:

[NIH Diversity Policy](#)

[FDA Diversity Guidance](#)

For the prospective section, based on the effect sizes of the mandibular advancement device (MAD) based on past meta-analyses, we conducted a GPower which revealed that obtaining a sample size of 45 participants would provide us 80% power to detect the anticipated effects. To compensate for dropout/attrition, we aim to recruit 50 participants.

No specific population will be targeted in terms of sex/gender or racial/ethnic background. The age range considers patients between 18 and 80 y.o. with a diagnosis of obstructive sleep apnea (OSA). Participants will be recruited from the consecutive patients referred to the Orofacial Pain Clinic for the management of OSA with a MAD.

Inclusion criteria:

- Age: >18 and <80 years old.
- No history of previous use of a MAD.
- Diagnosis of OSA by a sleep physician based on a PSG or HSAT (done >12 months before - evaluation date or > 12 months with >10% variation of BMI).
- Upon clinical examination: >8 teeth per arch; range of anteroposterior mandibular mobility >5 mm.
- Informed consent to participate in the study.

Exclusion criteria:

- Patients with concomitant diagnosed sleep disorders (i.e. insomnia, narcolepsy, restless legs syndrome, rapid eye movement sleep behavior disorder).
- History of previous allergic reaction to the appliance material (Polyamide 12).
- Patients using combination therapy for the management of OSA (i.e. PAP therapy or positional therapy).
- Upon clinical examination: periodontal disease (>4 mm on periodontal probing, with bleeding on probing, visual signs of periodontal inflammation); tooth horizontal mobility >1 mm, vertical mobility, and unfavorable crown to root ratio; open cavities, loose or fractured restorations, or patient undergoing restorative dental treatments.

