Advertising	DENT-036_flyer.pdf
Advertising	DENT-036 social media.pdf
Advertising	DENT-036_flyer_stamped.pdf

Research Procedures

Describe how the research will be conducted.

- What experience will study participants have?
- What will study participants be expected to do?
- How long will the study last?
- Outline the schedule and timing of study procedures.
- Provide visit-by-visit listing of all procedures that will take place.
- Identify all procedures that will be carried out with each group of participants.
- Describe deception and debrief procedures if deception is involved.

Differentiate between procedures that involve standard/routine clinical care and those that will be performed specifically for this research project. List medications that are explicitly forbidden or permitted during study participation.

PROSPECTIVE SECTION:

An Orthoapnea NOA® (OrthoApnea® laboratory, Malaga, Spain; FDA K202651) appliance will be custom made for each participant. Digital impressions (scanner 3Shape TRIOS® 3 (does not involve any form of radiation)), protrusive records will be obtained at 50% from maximum retrusion (5 mm fork and George GaugeTM, and clinical pictures will be obtained following the protocol recommended by the manufacturer. Maximum opening will be measured adding the interincisal distance to the overbite (in millimeters, using TheraBite® Range of Motion ruler). Information will be uploaded in the laboratory software (Apneadock®) to order the appliance. The MAD will be fabricated at an initial protrusion of 50%, with subsequent progressive mandibular components of additional 10% of protrusion until 80% of the maximum protrusive is achieved. Lastly, a full coverage morning deprogrammer (TAP® AM Aligner - Airway Management Inc) will be fabricated for all the participants to be used for 10 minutes upon removal of the MAD. Verbal and written instructions will be provided.

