Aim 1.1 was to assess the efficacy of the NOA® mandibular advancement device. To do this, we had two different criteria for success as defined before. For each of these criteria, we calculated the proportion of patients who “succeeded” vs. “failed.” As exploratory analyses, we used independent samples t-test or chi-square testes (as appropriate) to compare baseline demographic characteristics between those who succeeded and failed for each of the criteria. **Aim 1.2** was to describe the percentage of advancement (%) needed to reach efficacy for the NOA® appliance in the management of obstructive sleep apnea. For this aim, we only examined the data of those who “succeeded” in Aim 1.1. Paired samples t-tests were carried out to detect the possible statistically significant differences in each of the parameters studied before and after receiving the treatment. The sociodemographic characteristics and other variables of interest of the patients included in the prospective and retrospective studies were described (n, mean \pm SD).

Aim 2 was to describe patient compliance to the NOA® device in the management of obstructive sleep apnea. Using the definition of compliance provided above, we computed the proportion of study participants who complied with the NOA® appliance and described the use in terms of nights per week and hours per night (n, mean \pm SD).

Aim 3 was to assess the incidence and prevalence of temporomandibular disorder (TMD) diagnoses, morning headaches, possible sleep bruxism, nighttime voids, sleep quality, side effects, and of problems related to the NOA® appliance during the titration process by using paired samples t-test or chi-square testes (as appropriate) to compare baseline and final values between those who succeeded and failed for each of the criteria.

Mean and standard deviation and other centralization measures were calculated for quantitative variables, frequencies, and percentage values were calculated for categorical variables. The McNemar test was used as a significance test, with which assessed if there were significant changes. Statistical significance was defined by $p < 0.05$. All analyses were conducted using SPSS version 29.

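### Aim 1.2 pools advancement over OSA severity and the comparison with other designs is not adjusted for it, so case mix could pass for a device effect

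*Combined protocol and SAP*

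**What the plan says.** All references are to the combined protocol and SAP.

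- **Background, earlier devices.** Effective protrusion is described as highly variable, "ranging from 50% to 80% of maximal protrusion". On severity: "In mild to moderate cases of OSA, no differences were found between 50% and 75% of protrusion [5], whereas in severe cases" the higher setting did better.
- **Background, NOA.** The device "is thought to require a less degree of advancement to be effective in the management of OSA than other designs". This is stated for OSA in general, without reference to severity.
- **Research Procedures, prospective section.** "The MAD will be fabricated at an initial protrusion of 50%, with subsequent progressive mandibular components of additional 10% of protrusion until 80" per cent of the maximum is reached. No level below 50% can be observed.
- **Eligibility.** The disease criterion is "Diagnosis of OSA by a sleep physician based on a PSG or HSAT". There is no AHI range, and the retrospective cohort uses the same criteria.
- **Statistical Methods, Aim 1.2.** The aim is to "describe the percentage of advancement (%) needed to reach efficacy for the NOA® appliance in the management of obstructive sleep apnea", using only patients who succeeded under Aim 1.1. No breakdown by baseline severity is given.
- **Objectives.** Objective 1 adds a retrospective comparison with other designs. The retrospective extract lists OSA diagnosis, AHI, RDI and the advancement recorded before the follow-up sleep study. Statistical Methods describes the characteristics of both cohorts but gives no test, stratification or adjustment for comparing them.

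**The concern.** The plan cites evidence that severity changes how much advancement matters, then summarises advancement as if severity did not matter. Two things follow.

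First, a pooled NOA figure is hard to interpret. If most successes have mild to moderate disease, a figure near the 50% starting level is roughly what the cited finding would lead one to expect of other devices too.

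Second, the comparison is open to confounding by case mix. The comparator patients started therapy between 2010 and August 2021 and had a second sleep study. NOA patients are current referrals, people telephoned because they never started treatment, and respondents to advertising and registries. Nothing in the plan makes the severity mix of these groups alike.

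At stake is the claim that motivates the study: that this design achieves control with less advancement than others.

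**Working it through.** **What can be reproduced.** The plan gives no expected advancement, SD, severity mix or retrospective sample size, so it has no figure on this point to reproduce. Its sample size (33 participants in Statistical Methods, 45 in the study population section) rests on a treatment effect size and does not concern advancement. I use 33 per cohort below only as a convenient size.

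**Assumed inputs (not in the documents).** Mean advancement needed is 55% in mild to moderate and 70% in severe OSA, the same for both devices. The SD within a stratum is 10 points. The severe share is 20% in NOA and 40% to 60% in the comparator.

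**Step 1: case mix with identical devices.** Cohort mean = 55 + 15 × severe share.

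| Severe share | Cohort mean |
|---|---|
| 20% (NOA) | 58 |
| 40% (comparator) | 61 |
| 60% (comparator) | 64 |

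The false NOA advantage is 61 − 58 = 3 points, or 64 − 58 = 6 points. In general it is (gap between strata) × (difference in severe share). With a gap of 10 points the range is 2 to 4; with a gap of 20 it is 4 to 8. If NOA has the larger severe share, the sign reverses and a real saving could be hidden.

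**Step 2: could such an artefact look convincing?** Cohort SD = sqrt(10² + p(1 − p) × 15²), which is 11.7 at p = 0.2 and 12.4 at p = 0.4 or 0.6; the pooled value is about 12.0. A two-sided 5% t-test with 33 per cohort would call the 3-point artefact significant about 17% of the time and the 6-point artefact about 51%, against a nominal 5%. The plan specifies no such test; this shows only what an unadjusted comparison would risk.

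**Step 3: dilution, under a stronger assumption.** Suppose NOA saves 10 points in severe OSA and nothing elsewhere. With 20% to 40% severe, the pooled difference is 10 × 0.2 = 2 to 10 × 0.4 = 4 points. The zero in mild to moderate OSA is an input here, not a finding.

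**Step 4: adjust or restrict?** Suppose instead a saving of 5 points in mild to moderate and 10 in severe OSA. A severity-adjusted comparison of everyone then estimates 5(1 − p) + 10p = 6 to 7 points for p = 0.2 to 0.4. With SD 10 and 33 per cohort, power is about 67% to 80%. The severe stratum alone (7 to 13 per cohort, 10 points) has about 41% to 69%. Keeping all patients is better in this case.

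**Step 5: precision in the severe stratum.** Half-width = t(0.975, n − 1) × 10 / sqrt(n).

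| Patients | Severe (20% to 40%) | Half-width, severe | Half-width, all |
|---|---|---|---|
| 33 | 7 to 13 | 9.2 to 6.0 | 3.5 |
| 50 | 10 to 20 | 7.2 to 4.7 | 2.8 |

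These are best cases. The figures 33 and 50 count participants, and Aim 1.2 keeps only successes.

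**The case against.** A reader might infer that other devices work as well at 50% as at 75% in mild to moderate OSA, so that only severe patients can test the hypothesis, the rest should be set aside and no pooled comparison should be given. The documents do not support this.

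- Finding no difference between two settings in one cited study is not equivalence, and says nothing about the level each patient needs. The same paragraph gives effective protrusion as "ranging from 50% to 80% of maximal protrusion".
- The comparator is the advancement actually recorded in clinic, which may exceed 50% in mild to moderate disease. A lower NOA level could be seen there.
- Titration follows symptoms and the Epworth score, with the sleep test afterwards. Advancement at success may therefore track AHI severity less closely than the 55/70 assumption implies.

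It can also be said that Aim 1.2 is descriptive, covers NOA only and is limited to successes, and that no advancement test between cohorts is specified. That is correct. The power figures above therefore do not describe a planned analysis, and the unspecified comparison is a gap in its own right.

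These points remove any rule that judges the hypothesis in severe patients alone. They do not rescue an unstratified figure: if mild to moderate patients do carry information, severity still has to be separated from device before it can be read.

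**Conclusion.** The point holds in moderate form. By the plan's own evidence, severity modifies the effect of advancement; the 50% starting level probably leaves most room for a saving in severe OSA; and neither Aim 1.2 nor the Objective 1 comparison takes severity into account. A low pooled NOA figure would not distinguish a better design from a milder case mix.

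The illustrative size is a false advantage of 3 to 6 points, small beside the 50% to 80% range but enough to mislead when devices move in 10% steps. It depends on the assumed 15-point gap between strata and on a 20 to 40 percentage-point imbalance in severe share, neither of which the documents supply. The need for stratified reporting does not depend on those values. The change should be made; the point does not invalidate the study.

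**What to change.** 1. In Aim 1.2, report advancement at success separately for severe and for mild to moderate OSA, by baseline AHI, with number and 95% interval in each. State the AHI cut-off for severe disease, because the Background gives none.
2. For any comparison of advancement with other designs, stratify by or adjust for baseline AHI and keep all patients. Show the severity distribution of both cohorts beside the result.
3. Do not rest the conclusion on an unadjusted pooled figure.
4. Specify that the retrospective extract includes AHI from the study before treatment; it lists AHI without saying from which study.

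The cost is one split of a table and two or three sentences in Statistical Methods. No new visit or measurement is needed, and no patient's management changes. The downside is a small severe stratum with a wide interval, roughly ±5 to ±9 points at an assumed SD of 10 and wider once failures are excluded. The report should show it openly.
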